
38. Cornell RF, [name] SZ, Engelhardt BG, et al. Prospective Study of Apixaban for Primary Prevention of Venous Thromboembolism in Patients with Multiple Myeloma Receiving Immunomodulatory Therapy. *Blood.* 2018;132(Suppl 1):1233.

41. [name] G, Rosenbaum EJ, Pendergast W, et al. Physician Alerts to Prevent Symptomatic Venous Thromboembolism in Hospitalized Patients. *Circulation.* 2009;119(16):2196–201.

42. [name] G, Anderson FA, Ortel TL, et al. Randomized Trial of Physician Alerts

for Thromboprophylaxis after Discharge. Am J Med. 2013;126(5):435–42.

Table 8. Study Calendar

Procedure	Screening	12-Month Follow-Up
Informed Consent	X	
Inclusion/Exclusion	X	
Demographics	X	
Medical History	X	
Prior/Concomitant Medications	X	
Urine Pregnancy (if clinically indicated)	X	
Cardio-vascular History	X	
Thrombosis Evaluation		X
Bleeding Evaluation		X
Pill Diary Collection		X

Case Report Form

Screening	
Inclusion criteria (all must be checked)	
 Age \geq 18 years  Objectively-confirmed DVT and/or PE  Treated for at least 3 months with standard therapeutic anticoagulant therapy  Has not suffered symptomatic recurrence during prior anticoagulant therapy  Outpatient follow-up at BWH  Willing to provide written informed consent
 
AND have at least one of the following persistent provoking VTE risk factors:
 
 Persistent immobility (defined as paralysis, other inability to ambulate freely, bed-bound, wheelchair-bound)  Obesity (defined as $\text{BMI} \geq 30 \text{ kg/m}^2$)  Heart failure (systolic, diastolic, or combined)  Chronic lung disease (COPD, asthma, interstitial lung disease)  Chronic kidney disease ($\text{eGFR} < 60 \text{ mL/min/1.72m}^2$)  Chronic inflammatory/autoimmune disorder (inflammatory arthritis, vasculitis, inflammatory bowel disease, chronic infection)  Atherosclerotic cardiovascular disease (coronary, cerebrovascular, or peripheral artery disease) (up to 35% in each study group may have atherosclerotic cardiovascular disease as a qualifying persistent risk factor)

Exclusion criteria (NONE must be checked)	
 Women who are pregnant or breastfeeding  Women of child-bearing potential who are unwilling or unable to use an acceptable method of birth control (such as oral contraceptives, other hormonal contraceptives [vaginal products, skin patches, or implanted or injectable products], or mechanical products such as an intrauterine device or barrier methods [diaphragm, condoms, spermicides]) to avoid pregnancy for the entire study  Active cancer within the past 5 years  Contraindication to antithrombotic or antiplatelet therapy  Requirement for ongoing anticoagulant therapy (including atrial fibrillation with a CHADS_{VASC} > 1, diagnosed antiphospholipid antibody syndrome/deficiency of protein C,

	
S, or antithrombin), dual antiplatelet therapy, P2Y12 inhibition, or aspirin at a dose of >81 mg daily
 
[] Hemoglobin level < 9 mg/dL, a platelet count < 100,000/mm³, a serum creatinine level > 2.5 mg/dL, an ALT or AST level > 2 times the upper limit of the normal range, or a total bilirubin level > 1.5 times the upper limit of the normal range
 
[] History of a platelet disorder such as Von Willebrand Disease
 
[] History of bleeding diathesis or have had recent active bleeding
 
[] Active hepatobiliary disease
 
[] More than 6 months that have elapsed without taking an anticoagulant or low-dose aspirin
 
[] Known severe thrombophilia (any increased titer antiphospholipid antibody or positive lupus anticoagulant/DRVVT or deficiency of antithrombin, protein C, or protein S)
 
[] Life expectancy < 12 months or hospice care
 
[] Prisoners or subjects who are involuntarily incarcerated
 
[] Subjects who are compulsorily detained for treatment of either a psychiatric or physical (e.g., infectious disease) illness
 
[] Receiving concurrent non-FDA-approved or investigational agents or has received an investigational agent within the past 30 days prior to the first dose of study treatment (with the exception of approved medications being used for an approved indication, e.g., investigating a new dosing regimen for an approved indication).
 
[] Any condition, which in the opinion of the investigator, would put the subject at an unacceptable risk from participating in the study
 
[] Any other medical, social, logistical, or psychological reason, which in the opinion of the investigator, would preclude compliance with, or successful completion of, the study protocol

STOP HERE AND DO NOT ENROLL PATIENT IF ANY OF THE INCLUSION CRITERIA ARE ABSENT OR ANY EXCLUSION CRITERIA ARE PRESENT
	
Eligible	[] Yes [] No
Written informed consent signed	[] Yes [] No

Patient Demographics	
Study ID number	-----
Date of enrollment	____ / ____ / ____ MM DD YYYY
Date of birth	____ / ____ / ____ MM DD YYYY
Gender	 Male  Female
Ethnicity	 Hispanic/Latino  Non-Hispanic/Non-Latino
Race	 American Indian or Alaskan Native  Asian  White  Hispanic or Latino  Native Hawaiian or Pacific Islander  Black or African-American  Mixed race  Other, specify: _____
BMI calculated	_____ (kg/m ²)

Venous Thromboembolism Characteristics***	
***Patient may have both PE and DVT; if so complete both fields	
Deep Vein Thrombosis	DVT confirmed by imaging (ultrasound, CT, MRI, or venogram)  Yes  No
	Date of imaging diagnosis ____ / ____ / ____ MM DD YYYY
	Site of DVT  Upper extremity  Pelvic vein  Leg  Proximal with calf  Proximal without calf  Calf only

	[] Other (describe): _____
Pulmonary Embolism	PE confirmed by:  Ventilation perfusion scan  Chest CT  Contrast pulmonary angiogram Hypotension, shock, cardiac arrest or respiratory failure as presenting sign of PE:  Yes  No RV dysfunction  Yes  No Diagnosed by:  CT  Echocardiogram Positive cardiac biomarker (troponin or BNP)  yes  no
	Date of imaging confirmed diagnosis _____ / _____ / _____ MM DD YYYY
	Both PE and DVT present  Yes  No
	Symptomatic DVT or PE  Yes  No
	Advanced therapy for VTE  Inferior vena cava filter  Thrombolytic therapy for PE  Catheter thrombectomy for DVT  Catheter direct therapy for PE  Surgical thrombectomy for DVT  Surgical embolectomy for PE
	Outpatient VTE treatment history  LMWH monotherapy  Fondaparinux  Direct oral anticoagulant  Warfarin Duration of anticoagulation: _____ months (enter number out to the tenth place and round-up; for example 3.48 months would be 3.5 months)

Persistent Provoking VTE Risk Factors	
Persistent provoking VTE risk factors (patient must have at least one but can have multiple; record all that apply)	 Persistent immobility (defined as paralysis, other inability to ambulate freely, bed-bound, wheelchair-bound)  Obesity (defined as BMI ≥ 30 kg/m ²)  Heart failure (systolic, diastolic, or combined)  Chronic lung disease (COPD, asthma, interstitial lung disease)  Chronic kidney disease (eGFR <60 mL/min/1.72m ²)  Chronic inflammatory/autoimmune disorder (inflammatory arthritis, vasculitis, inflammatory bowel disease, chronic infection)  Atherosclerotic cardiovascular disease (coronary, cerebrovascular, or peripheral artery disease) (up to 35% in each study group may have atherosclerotic cardiovascular disease as a qualifying persistent risk factor)

VTE Risk Factors and Comorbid Conditions	
Cardiovascular disease	 Cardiomyopathy/diminished left ventricular systolic function If yes, EF (%) _____  Heart failure with reduced EF  Heart failure with preserved EF (EF >50%)  Coronary artery disease If yes,  Prior CABG  Prior coronary stent(s)  Prior MI  History of unstable angina  Stable angina  Valvular heart disease  Atrial fibrillation or atrial flutter  Pulmonary hypertension
Hypertension	 Yes  No
Peripheral artery disease	 Yes  No

Carotid occlusive disease	 Yes  No
Prior cerebrovascular accident (strokes or TIAs)	 Yes  No
Family history of VTE	 Yes  No
Prior personal history of VTE (other than the event that made the patient eligible for this trial)	 Yes  No
Hypercholesterolemia	 Yes  No
Chronic liver disease (as noted in chart)	 Yes  No If yes, cirrhosis  yes  no
Cigarette smoking (check only 1)	 Current smoker  Former smoker  Never smoker
Major surgery within 3 months of VTE diagnosis	 Yes  No If yes, date MM / DD / YYYY
Prior hospitalization within 30 days of VTE diagnosis	 Yes  No
Chronic lung disease (COPD, asthma, pulmonary fibrosis, interstitial lung disease)	 Yes  No
Diabetes mellitus	 Yes

(Type I or II)	[] No	
Inflammatory arthritis (rheumatoid arthritis, psoriatic arthritis)	[] Yes	[] No
Inflammatory bowel disease (Crohn's Disease, Ulcerative Colitis)	[] Yes	[] No
Inherited thrombophilia	[] Yes	[] No If yes, indicate: [] Factor V Leiden (heterozygous or homozygous) [] Prothrombin gene mutation (heterozygous or homozygous)
Active use of oral contraceptive or hormone replacement at time of VTE diagnosis	[] Yes	[] No
Infectious illness requiring antibiotics or antiviral therapy within 3 months of VTE diagnosis	[] Yes	[] No
Serum creatinine >2.5 mg/dL	[] Yes [] No If yes, is patient on dialysis? [] Yes [] No	If yes, patient should not be enrolled.
Concomitant medications	
[] aspirin If yes, dose = ____ mg/daily
 
If >81 mg/daily, patient should not be enrolled.
 
[] daily NSAID use
	

Study Treatment Characteristics	
Randomization	 Oral Apixaban 2.5 mg twice daily  Oral placebo twice daily
Date study drug started	 /  /  MM DD YYYY
Date study drug stopped	 /  /  MM DD YYYY Completed full 12 months of study drug?  Yes  No If did not stay on drug for 12 months, reason why not?  Fulfilled criteria for a primary study outcome (recurrent VTE or major/clinically relevant non-major bleed)  Patient expired  Adverse drug event or side-effect  Change in clinical status (such as change in goals of care, comfort measures, hospice care)  Patient preference/withdrawal of consent
Medication adherence (via pill count)	Total doses taken/total doses prescribed = ( / 720) x 100 =  %

12-Month Study Outcomes	
Deep vein thrombosis	 Yes  No If yes, date  /  /  MM DD YYYY Confirmed by diagnostic imaging:  Yes  No If yes, by?  Ultrasound  CT  MRI  Venography

	
Location:
 
 Upper extremity
 
If checked:
 
 Bilateral or SVC
 
 Lower extremity
 
If checked:
 
 Bilateral or IVC
 
 Proximal (popliteal or higher)
 
 Calf
 
Hospitalized?
 
 Yes
 
 No
 
Treatment:
 
 Anticoagulation
 
 Pharmacomechanical (catheter-based) therapy
 
 Surgery
 
 IVC filter

Superficial vein thrombosis	
 Yes
 
 No
 
If yes, date _____ / _____ / _____ MM DD YYYY

Other venous thrombosis (mesenteric, cerebral sinus, gonadal, etc.)	
 Yes
 
 No
 
If yes, date _____ / _____ / _____ MM DD YYYY

Pulmonary embolism	
 Yes
 
 No
 
If yes, date _____ / _____ / _____ MM DD YYYY
 
Confirmed by diagnostic imaging:
 
 Yes
 
 No
 
If yes, by?
 
 CT
 
 MRI

	
 Pulmonary angiography  V/Q scan
 
Location:  Unilateral  Bilateral
 
RV dysfunction on echocardiogram or CT?  Yes  No
 
Positive cardiac biomarker?  Yes  No
 
Associated with hemodynamic or respiratory instability (respiratory failure, shock, hypotension, cardiac arrest)?  Yes  No
 
Fatal?  Yes  No
 
Hospitalized?  Yes  No
 
Treatment:  Anticoagulation  Systemic fibrinolysis  Pharmacomechanical (catheter-based) therapy  Surgical embolectomy  IVC filter

Death	
 Yes  No
 
If yes, date _____ / _____ / _____ MM DD YYYY
 
Cause of death:  PE  Myocardial infarction  Stroke

	
 Other cardiovascular  Cancer-related  Non-cardiovascular, non-cancer  Unknown
 
 CV Death: includes death due to PE, MI, stroke, other cardiovascular cause, or unknown

Major or clinically relevant non-major bleed	
 Yes  No
 
If yes, date   /   /   MM DD YYYY

Major bleed	
 Yes  No
 
If yes, date   /   /   MM DD YYYY
 
Location:
 
 Intracranial  Surgical/operative site  Gastrointestinal  Genitourinary  Retroperitoneal  Pericardial  Pulmonary  Other thoracic  Musculoskeletal  Nasopharyngeal  Hematocrit or hemoglobin decrease without clear source  Other
 
Fatal?
 
 Yes  No
 
Hospitalized?
 
 Yes  No
 
Associated with hemodynamically instability?
 
 Yes  No

	
Treatment:
 
 Blood products
 
 Surgery
 
 Invasive procedure
 
 Medical therapy (PCC, andexanet, etc.)

Clinically relevant non-major bleed	
 Yes
 
 No
 
If yes, date _____ / _____ / _____ MM DD YYYY
 
Location:
 
 Intracranial
 
 Surgical/operative site
 
 Gastrointestinal
 
 Genitourinary
 
 Retroperitoneal
 
 Pericardial
 
 Pulmonary
 
 Other thoracic
 
 Musculoskeletal
 
 Nasopharyngeal
 
 Hematocrit or hemoglobin decrease without clear source
 
 Other: _____
 
Hospitalized?
 
 Yes
 
 No
 
Treatment:
 
 Blood products
 
 Surgery
 
 Invasive procedure
 
 Medical therapy (PCC, andexanet, etc.)

Non-bleed adverse drug reaction	
 Yes
 
 No
 
If yes, date _____ / _____ / _____ MM DD YYYY
 
Type of reaction:
 
 Anaphylaxis

	
 Cutaneous (rash, etc.)  Liver function abnormalities  Other: _____
 
Hospitalized?  Yes  No
 
Study drug discontinuation?  Permanent stop  Temporary stop  Not discontinued

Myocardial infarction (defined as the presence of at least 2 of the 3 following conditions:
 
• The detection of a rise and/or fall of cardiac biomarkers, with at least one of the values being elevated [preferably cardiac troponin (cTn) with at least one value above the 99th percentile upper reference limit] and with at least one of the following:
(1) symptoms of myocardial ischemia;(2) new (or presumably new) significant ST-segment/T-wave changes or left bundle branch block;(3) development of pathological	
 Yes  No
 
If yes, date _____ / _____ / _____ MM DD YYYY
 
Type:  ST elevation  Non-ST elevation
 
Fatal?  Yes  No
 
Treatment:  Systemic fibrinolysis  Percutaneous coronary intervention (angioplasty, stenting, etc.)  CABG  Medical management

Q waves on ECG; (4) new loss of viable myocardium or regional wall motion abnormality by imaging; (5) identification of intracoronary thrombus by angiography or autopsy)
	

Non-MI coronary revascularization
	
 Yes  No
 
If yes, date _____ / _____ / _____ MM DD YYYY
 
Recascularization:
 
 Percutaneous coronary intervention (angioplasty, stenting, etc.)  CABG


Stroke/TIA (defined as a new, focal neurologic deficit of sudden onset, lasting at least 24 hours, not due to a readily identifiable nonvascular cause (i.e. brain tumor, trauma), as confirmed by a neurologist and neuroimaging.)
	
 Yes  No
 
If yes, date _____ / _____ / _____ MM DD YYYY
 
Confirmation (both must be present):
 
 By neurologist  By neuroimaging
 
TIA?  Yes  No
 
Stroke?  Yes  No
 
If yes, type of stroke:  Ischemic

Appendix

1. [Apixaban Package Insert](https://packageinserts.bms.com/pi/pi_eliquis.pdf) (Version June 2018)
https://packageinserts.bms.com/pi/pi_eliquis.pdf
2. [Eliquis Medication Guide](https://packageinserts.bms.com/medguide/medguide_eliquis.pdf)
https://packageinserts.bms.com/medguide/medguide_eliquis.pdf
3. Informed Consent Form

**Randomized Controlled Trial of Extended-Duration Low-
Dose Apixaban to Prevent Recurrence in High-Risk
Patients with Provoked Venous Thromboembolism
(HI-PRO Trial)**

Final version

BMS Protocol #: CV185-745

Protocol Version Date: 11/19/2021

Sponsor:
[name], MS
Brigham and Women's Hospital
Cardiovascular Division
[name]
[name]
[contact] (Phone)
[contact] (Fax)
[contact]

Table of Contents

Protocol Summary	3
Study Flow Diagram	4
Study Subject Contact Calendar:	5
Abbreviations and Definitions	6
Study Contacts	8
Specific Aims.....	11
Introduction and Background	13
Rationale for the Proposed Study and Trial Design.....	15
Study Objectives	19
Study Design.....	19
Study Duration.....	19
Study Population.....	19
Study Inclusion Criteria.....	20
Study Exclusion Criteria.....	21
Screening Procedures.....	24
Treatment Description	25
Safety Outcomes	26
Efficacy Outcomes.....	26
Drug Accountability.....	28
Follow-Up	29
Safety Monitor	30
Assessment and Reporting of Adverse Events	30
Data Reporting, Processing, and Quality Control.....	40
Monitoring Plan	41
Statistical Methods.....	49
Interim Analysis.....	55
Investigator Responsibilities.....	56
Feasibility.....	57
Potential Risks and Benefits	60
Ethical Considerations	63
References.....	64
Case Report Form	70
Appendix.....	85

Protocol Summary

Title: Randomized Controlled Trial of Extended-Duration Low-Dose Apixaban to Prevent Recurrence in High-Risk Patients with Provoked Venous Thromboembolism (HI-PRO Trial)

Design: U.S.-based, single-center, randomized placebo-controlled trial.

Brief Treatment Description: Low-dose apixaban (2.5mg twice daily) for extended-duration secondary prevention of VTE after initial treatment for provoked VTE.

Purpose: To establish the safety and efficacy of low-dose apixaban versus placebo for extended prevention of recurrence after provoked VTE in patients with at least one persistent provoking factor.

Population: Outpatients with provoked VTE with at least one persistent provoking factor.

Enrollment: 600 subjects

Randomization: 1:1

Clinical Site Locations: 1 center (Brigham and Women's Hospital)

Study Duration: 36 months; enrollment period of up to 20 months with 12-month follow-up.

Primary Safety and Efficacy Outcomes:

Primary Safety Outcome: International Society on Thrombosis and Haemostasis (ISTH) major bleeding at 12 months.

Primary Efficacy Outcome: Symptomatic, recurrent VTE, defined as the composite of deep vein thrombosis and/or pulmonary embolism at 12 months.

[figure not shown]
Secondary Safety Outcome: ISTH clinically relevant non-major bleeding at 12 months.

Secondary Efficacy Outcome: The composite of death due to cardiovascular cause, nonfatal myocardial infarction, stroke or systemic embolism, critical limb ischemia, or coronary or peripheral ischemia requiring revascularization (major adverse cardiovascular events, including major adverse limb events) at 12 months.

Follow-Up: Follow-up will consist of Electronic Health Record (EHR) review at 12-months from study enrollment.

Interim Analysis: An interim analysis for the primary safety and efficacy outcomes will be performed when 300 subjects have completed 12-month follow-up.

Study Flow Diagram

DVT, deep vein thrombosis; PE, pulmonary embolism; VTE, venous thromboembolism

Figure 1. Study flow-diagram for a single-center, randomized placebo-controlled trial of extended low-intensity apixaban for high-risk provoked VTE.

Study Subject Contact Calendar:

Date	Event	Study Drug
Enrollment (Month 0)	Subject will be consented by study physician and randomized through the Investigational Drug Service computer randomization program.	3 months of study drug (apixaban or placebo) will be given during this visit or sent to subject within 2 business days of the enrollment visit via mail or courier.
Month 3	Study nurse check-in	First 3 months drug containers and unused drug collected via mail and returned to pharmacy for proper disposal, 3 additional months' worth of medication will be given or sent to subject.
Month 6	Study nurse check-in	Drug containers and unused drug collected via mail and returned to pharmacy for proper disposal, 3 additional months' worth of medication will be given or sent to subject.
Month 9	Study nurse check-in	Drug containers and unused drug collected via mail returned to pharmacy for proper disposal, 3 additional months' worth of medication will be given or sent to subject.
Month 12	End-of-treatment visit	All remaining medications, drug containers, and 12-month drug diary will be collected.

Abbreviations and Definitions

Listed in alphabetical order

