Routine laboratory testing is neither recommended nor required in patients receiving extended duration apixaban, including the 2.5 mg twice daily dosing regimen. Patients enrolled in the study will either have been identified from one of the practices of our Vascular Medicine faculty or will be assigned to one of our faculty for long-term management of VTE. Accordingly, every patient enrolled in the study will have ongoing medical care with a dedicated Vascular Medicine provider. Study patients will be encouraged to follow-up with their primary care, , and other appropriate clinicians. Specifically, at the end of the treatment visit, every patient will be reminded to follow-up with a PCP as dictated by routine care and best clinical practice. Demographic, clinical characteristics, medication records, and outcomes will be abstracted from the BWH Electronic Health Record (EPIC).

When our Research Nurse conducts the every 3-month telephone call in advance of releasing a 3-month allotment of study drug or placebo the subject will be queried for any issues with the study or adverse events.

We will conduct an end-of-treatment visit to obtain data relevant to the study end points.

We will assess medication adherence via pill count. Medication adherence will be calculated in three month intervals as the total number of doses taken divided by the total number of doses prescribed for that time period ($[x / 180] \times 100$ = medication adherence [%]) and also for the total 360-day study period ($[x / 720] \times 100$ = medication adherence [%]). Subjects will be given a study drug diary to fill out at home each day. Subjects will write down the time they take their study drug and any side effects. The study drug diary will be collected at a regularly scheduled office visit or the end-of-treatment visit at conclusion of the study period.

Subject Retention, Withdrawal, and Termination

Continued participation of study subjects will be encouraged at the time of outpatient evaluation through the 12-month follow-up interval. However, study subjects will be informed that they retain the right to withdraw from the study at any time without compromise to their current or subsequent medical care. Subjects will be terminated from the study if they expire or elect to withdraw.

If study subjects elect to withdraw, they will be asked for permission to do the following:

1. Be contacted by telephone **AND**
2. Have their physicians contacted

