Adverse events can be spontaneously reported or elicited during open-ended questioning, examination, or evaluation of a subject. (In order to prevent reporting bias, subjects should not be questioned regarding the specific occurrence of one or more adverse events).

All SAEs that occur following the subject's written consent to participate in the study through 30 days of discontinuation of dosing will be reported to BMS Worldwide Safety.

Serious Adverse Events

A serious adverse event (SAE) is any untoward medical occurrence at any dose that:

- results in death
- is life-threatening (defined as an event in which the subject was at risk of death at the time of the event; it does not refer to an event which hypothetically might have caused death if it were more severe)
- requires inpatient hospitalization or causes prolongation of existing hospitalization
- results in persistent or significant disability/incapacity
- is a congenital anomaly/birth defect
- is an important medical event, defined as a medical event that may not be immediately life-threatening or result in death or hospitalization but, based on appropriate medical and scientific judgment, may jeopardize the subject or may require intervention (e.g., medical, surgical) to prevent one of the other serious outcomes listed above. Examples of such events include but are not limited to intensive treatment in an emergency department or at home for allergic bronchospasm; blood dyscrasias or convulsions that do not result in hospitalization.

Suspected transmission of an infectious agent (e.g., pathogenic or non-pathogenic) via the study drug is an SAE. Although pregnancy, overdose, and cancer are not always serious by regulatory definition, these events must be handled as SAEs.

The following hospitalizations are not considered SAEs:

- A visit to the emergency room or other hospital department lasting less than 24 hours that does not result in admission (unless considered an "important medical event" or a life-threatening event)
- Elective surgery planned before signing consent
- Admissions as per protocol for a planned medical/surgical procedure
- Routine health assessment requiring admission for baseline/trending of health status (e.g., routine colonoscopy)
- Medical/surgical admission other than remedying ill health state that was planned before study entry. Appropriate documentation is required in these cases

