reduction (75%) in recurrent VTE as low-intensity rivaroxaban (10 mg daily) compared with low-dose aspirin (2). The 75% relative risk reduction was reported specifically for recurrent VTE and in the provoked VTE patient population, comparing rivaroxaban 10 mg daily versus low-dose aspirin. This relative risk reduction specifically pertains to our primary study outcome and our exact patient population and comes from a robust randomized controlled trial analysis. If anything, the reduction in the proposed study should be even greater since we propose a placebo-control instead of active (aspirin) control and we will be following our patients for 12 months, instead of allowing shorter follow-up as was reported in EINSTEIN CHOICE. Accordingly, assuming an estimated incidence in the placebo group of 6% at 12 months and a decrease in the primary outcome of 75% with apixaban 2.5 mg twice daily as compared with placebo, we calculated that we would need to enroll 279 patients in each group for the study to have 80% power to show the superiority of low-intensity apixaban over placebo, at a two-sided alpha level of 0.05. To account for patients who may be lost to follow-up or withdraw from the study, we will recruit 300 in each arm and 600 total.

EINSTEIN-CHOICE enrolled patients after a required 6 to 12 months of anticoagulant therapy. Our study requires that patients complete at least 3 months of anticoagulant therapy in accordance with current and widely-accepted evidence-based clinical practice guidelines (Eur Heart J. 2020; 41: 543–603, Chest. 2016;149:315-352, and Circulation. 2011;123:1788–1830). Data from the PADIS-PE study showed that the rate of VTE recurrence is higher closer in temporal proximity to the initial event, such that the recurrence rate is higher at 3-6 months after diagnosis than it is at 6-12 months (Couturaud F, et al. Six Months vs Extended Oral Anticoagulation After a First Episode of Pulmonary Embolism. JAMA. 2015;314(1):31-40). Accordingly, the anticipated event rate should be higher in our study than EINSTEIN-CHOICE and the resultant observed relative risk reduction is likely to be higher.

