- Musculoskeletal and connective tissue disorders: muscle hemorrhage
- Reproductive system and breast disorders: vaginal hemorrhage, metrorrhagia, menometrorrhagia, genital hemorrhage
- Vascular disorders: hemorrhage
- Skin and subcutaneous tissue disorders: ecchymosis, skin hemorrhage, petechiae
- Eye disorders: conjunctival hemorrhage, retinal hemorrhage, eye hemorrhage
- Investigations: blood urine present, occult blood positive, occult blood, red blood cells urine positive
- General disorders and administration-site conditions: injection-site hematoma, vessel puncture-site hematoma

Additional information about the risks of apixaban can be found in the Apixaban Med Guide (see Appendix).

Protection of Subjects against the Risks of Research Procedures

Before Study Enrollment

A rigorous screening process will be utilized to ensure that subjects with an increased risk of harm due to enrollment in the study are excluded from the study. This will include performing a detailed history and physical examination (to ensure that enrolled subjects truly fulfill all eligibility criteria) and carefully reviewing the results of laboratory testing (in particular, hematocrit, platelet count, INR, and serum creatinine).

During Follow-Up

Changes in health status during the 12-month follow-up period will be evaluated by the patient's primary physician, and other routine providers. All subjects enrolled will also have ongoing medical care with a dedicated Vascular Medicine provider. As apixaban is an FDA-approved drug commonly used for thromboprophylaxis and does not require routine follow-up clinical or laboratory monitoring for toxicity, the study will not mandate any follow-up visits or procedures other than those required for the patient's routine care.

Protection against Loss of Confidentiality

Subject confidentiality will be protected by maintaining all paper records in locked file cabinets in locked offices and all electronic records in password-protected computer files. All study data will be de-identified for storage in the electronic data repository. In addition, any identifying information will be removed from images or other data used in publication or presentations. All database information will be stored on computer systems that are located behind an electronic firewall, which will only permit access to certified study personnel. Access to study data files will be password-protected.

Use of Information and Publication

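### The protocol describes outcome capture inconsistently and writes no specific outcome questions or route to outside records, so some VTE or bleeding treated elsewhere could be missed

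*Combined protocol and SAP*

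**What the plan says.** All references are to the final protocol (11/19/2021) unless the SAP is named.

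**Text that points to the record, or to no study visits**
- Protocol Summary, Follow-Up: "Follow-up will consist of Electronic Health Record (EHR) review at 12-months from study enrollment".
- Follow-Up Evaluation: "outcomes will be abstracted from the BWH Electronic Health Record (EPIC".
- Potential Risks and Benefits, During Follow-Up: "the study will not mandate any follow-up visits or procedures", with an exception for what routine care requires. The Feasibility section likewise advertises the absence of study-mandated office visits.

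**Text that points to active contact**
- The Study Subject Contact Calendar lists nurse check-ins at months 3, 6 and 9 and an end-of-treatment visit at month 12.
- Follow-Up Evaluation: "We will conduct an end-of-treatment visit to obtain data relevant to the study end points".
- Table 8 (Study Calendar) marks a thrombosis evaluation and a bleeding evaluation at 12 months.
- Serious Adverse Event Collecting and Reporting adds reports from subjects and care providers, and Epic alerts for admissions and emergency visits.

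**What patients are asked**
- The 3-monthly call is a general query about problems with the study or adverse events.
- Definitions, Adverse events: "subjects should not be questioned regarding the specific occurrence of one or more adverse events". The stated aim is to prevent reporting bias. Documentation of Adverse Events repeats the preference for non-directed questions.

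**The concern.** The primary outcome is symptomatic recurrent VTE and the primary safety outcome is major bleeding. Either can take a patient to the nearest hospital, and the Feasibility section describes a clinic population drawn from Boston, its suburbs and New England. An event treated elsewhere reaches the trial only if the patient or a provider reports it, or if it shows in the centre's record.

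The contacts that could find such events already exist, but nothing written makes them ask. The protocol defines an adverse event as any new untoward medical occurrence, which on its face includes VTE and bleeding. A nurse following the rule against specific questions would therefore not ask about either on the calls. The month-12 evaluations have no stated questions or form. The endpoints committee is to receive the relevant documentation, but no section says how records from another hospital are obtained. Permission to contact a subject's physicians is mentioned only for those who withdraw.

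SAP 4.2.2 sets censoring at the last contact date. A patient who stays in contact and whose outside event is never learned of is analysed as event-free. That lowers observed event rates and costs power. For clinically relevant non-major bleeding, whose definition includes discomfort or impaired daily activities, a chart may show nothing unless the patient is asked.

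**Working it through.** **1. The text.** Taken literally, a follow-up that consists of record review, with no visits mandated beyond routine care, does not fit with a scheduled month-12 visit held to collect endpoint data. Only the Protocol Summary and Follow-Up Evaluation name the record as the source; the risk section speaks of visits. No section gives fixed VTE or bleeding questions, a procedure for outside records, or an allowance for missed events.

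**2. Inputs** (protocol, Sample Size Calculation)
- Test: Pearson chi-squared (consultant's output), "at a two-sided alpha level of 0.05".
- Rates: "assuming an estimated incidence in the placebo group of 6% at 12 months and a decrease in the primary outcome of 75" per cent, so 6% on placebo and 6% × 0.25 = 1.5% on apixaban.
- Size: "we would need to enroll 279 patients in each group for the study to have 80% power"; the consultant's output gives power 0.8005.
- Recruitment: 300 per arm. 279/300 = 0.93, a 7% allowance assigned to loss to follow-up and withdrawal.
- Missed share: not in the documents. Assumed 5% to 30%, equal in both arms.

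**3. Formula.** With p̄ = (p₁ + p₂)/2,

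power = Φ{ [p₁ − p₂ − 1.96·√(2p̄(1 − p̄)/n)] / √([p₁(1 − p₁) + p₂(1 − p₂)]/n) }.

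**4. The plan's own figure.** At n = 279, p₁ = 0.06, p₂ = 0.015 and p̄ = 0.0375, the two standard errors are 0.01609 and 0.01597. Power = Φ[(0.045 − 1.96 × 0.01609)/0.01597] = Φ(0.84) = 0.8005, which matches. At n = 300 it is 0.828.

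**5. Missed events.** Multiply both rates by (1 − missed share). At 20% missed and n = 300, the rates are 4.8% and 1.2%, p̄ = 0.03, and the standard errors are 0.01393 and 0.01385. Power = Φ[(0.036 − 1.96 × 0.01393)/0.01385] = Φ(0.63) = 0.735.

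| Missed (assumed) | Rates | Power, 300/arm | Power, 279/arm | N/arm for 80% |
|---|---|---|---|---|
| 0% | 6.0% v 1.5% | 0.828 | 0.801 | 279 |
| 5% | 5.7% v 1.425% | 0.808 | 0.779 | 294 |
| 10% | 5.4% v 1.35% | 0.786 | 0.756 | 311 |
| 20% | 4.8% v 1.2% | 0.735 | 0.704 | 352 |
| 30% | 4.2% v 1.05% | 0.676 | 0.644 | 404 |

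At 300 evaluable per arm, power drops below 80% at about 7% missed. At 279 there is no margin, so practically any missed share does so.

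**6. Cross-check with SAP 6.1.** Power = Φ[√m·|λ − 1|/(λ + 1) − 1.96], with m = 300 × (0.06 + 0.015) = 22.5 expected events. At λ = 0.24 this gives 0.828 with none missed, 0.788 at 10% and 0.739 at 20% (m = 18). At λ = 0.20 it gives 0.885, 0.851 and 0.807, and falls below 80% by 25% missed (0.782).

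**7. Effect measures.** At 20% missed, the ratio is 1.2/4.8 = 0.25, the same as 1.5/6.0. The risk difference shrinks from 4.5 to 3.6 percentage points.

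**The case against.** A reader might infer that outcomes come only from the hospital's record and that nobody asks the patients. The documents do not support that. There are quarterly calls, a month-12 visit for endpoint data, 12-month thrombosis and bleeding evaluations, patient and provider reports, Epic alerts, and case report form items for each outcome. Every subject carries an alert card and has a Vascular Medicine provider at the centre. Returned drug, pill counts and diaries could also reveal that a patient stopped study drug after an event elsewhere. Symptomatic VTE confirmed by imaging is something many patients would volunteer to an open question.

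A reader might also infer that the rule against specific questions stops the trial from finding its own endpoints. It is written for adverse events, and no section expressly applies it to the month-12 visit.

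On size, no missed share is documented, and 5% missed still leaves 0.808 at 300 per arm. At the 8.2% placebo rate in the consultant's last calculation, 20% missed leaves about 0.862 at 300 per arm and 0.836 at 279.

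These points stand, and they limit the claim. They do not remove it: the listed routes reduce the risk, but none supplies fixed outcome questions or a way to obtain outside records, and the sections on visits still conflict.

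**Conclusion.** The concern holds in a limited form. The follow-up sections contradict one another on whether there is a study visit at month 12 and on where outcomes come from. The calls as written are general, the adverse-event rule read with its own definition covers VTE and bleeding, and no route to outside records is written. Some events treated elsewhere could be missed.

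The power loss is conditional on a missed share that the documents do not give. With 300 evaluable per arm and equal misses, it is about 2 points at 5% missed and about 15 points at 30%, with 80% lost from about 7%. This rests on the planning rates of 6% and 1.5%; higher rates or the stronger SAP hazard ratio leave more room.

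It would be wrong to read this as bias in the treatment effect. Equal misses in a double-blind trial leave the risk ratio about unchanged; the loss is in precision and in the absolute rates and difference. The figures apply to VTE alone, since no power is stated for bleeding. There the effect would be an understated rate and less chance of seeing a difference.

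**What to change.** 1. Reconcile the Protocol Summary, Contact Calendar, Follow-Up Evaluation, adverse-event Definitions, During Follow-Up and Table 8, so that one description says which contacts are required and where outcome data come from. Bring the Feasibility remark on visits into line.
2. State that the adjudicated outcomes are exempt from the rule against specific questions. Blinding limits the reporting bias which that rule guards against.
3. Add fixed questions on VTE, bleeding, cardiovascular events and care outside the centre to the existing 3-monthly calls and the month-12 visit.
4. When a patient reports an event, request the outside records for the endpoints committee.

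The cost is a call script and wording changes, a few minutes per existing call and occasional record requests. No extra patients or visits are needed.
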